9.4. Study Termination

Every reasonable effort should be made to maintain protocol compliance and participation in the study. If a subject is withdrawn from the study for any reason, the reason will be recorded. If withdrawal is the result of a serious AE, the investigator will offer to arrange for appropriate specialist management of the problem and the Ethical committee will be informed in a timely manner. The extent of follow up will be determined by the investigator but will be at least for the whole study period. Subjects withdrawn prematurely for any reason will not be re-entered in to the trial, although they may be requested to return to the clinic for safety evaluation. A complete safety evaluation will be made for any subject who terminates from the study prematurely. Group 2 and 3 volunteers will also be offered the standard rabies immunisation at the end of the trial.

The following will result in study termination and will not be considered normal protocol completion:

- Development of an AE applies to a subject who is withdrawn from the study primarily due to a severe or serious adverse event.
- Lost to follow-up applies to a subject who consistently fails to return for protocol study visits, is not reachable by telephone or other means of communication and/or is not able to be located.
- Research terminated by investigator - the entire study is terminated by the investigator for any reason.
- Withdrawal of Consent applies to a subject who withdraws consent to participate in the study for any reason.
- Protocol deviation- applies to a subject who fails to achieve critical endpoints or did not meet entrance criteria but was enrolled into the study.
- Other is a category used when previous categories do not apply and requires an explanation.

10. STUDY PROCEDURES

10.1. Clinical Evaluations

Screening Visit:

Medical history and physical examination will be performed at screening to exclude any significant medical conditions as described in Section 5.2. HLA typing will also be performed on blood taken at this visit, as outlined in Section 10.3.

D0 (Vaccination with AdCh63 ME-TRAP)

Medical history, temperature monitoring +/- physical examination will be performed and eligibility will be reviewed by the Investigator prior to vaccination. Vaccine will be administered as outlined in Section 8.4. Venepuncture for exploratory immunology and *Plasmodium falciparum* polymerase chain reaction will be performed as outlined in Section 10.3. As outlined in Sections 4.3.2 and 10.3.2, *P. falciparum* PCR testing will be performed at a later stage, the results will be used in the interpretation of immunogenicity data, and this assay is not validated for clinical diagnostic purposes. As such, PCR results will have no impact on the conduct of the study.

D1, 2 and 3

Each volunteer will be visited at home daily for three days by a field worker for assessment and recording of any solicited and unsolicited AEs in the CRF. If necessary the volunteer will continue to be seen regularly until the symptom(s) have resolved or stabilised.

D14 (+/-7 days)

Medical history, temperature monitoring +/- physical examination will be performed and recorded in the CRF. Any solicited and unsolicited AEs will be recorded. Venepuncture will be performed for FBC, ALT, Creatinine and exploratory immunology as outlined in Section 10.3.

D56 (Vaccination with MVA ME-TRAP) (- 7/ +30 days)

Medical history, temperature monitoring +/- physical examination will be performed and eligibility will be reviewed by the Investigator prior to vaccination. Vaccine will be administered as outlined in Section 8.4. Venepuncture will be performed for FBC, ALT, Creatinine and exploratory immunology as outlined in Section 10.3.

D57, 58 and 59

Each volunteer will be visited at home daily for three days by a field worker for assessment and recording of any solicited and unsolicited AEs in the CRF. If necessary the volunteer will continue to be seen regularly until the symptom(s) have resolved or stabilised.

D63 (-1/+7 days)

Medical history, temperature monitoring +/- physical examination will be performed and recorded in the CRF. Any solicited and unsolicited AEs will be recorded. Venepuncture will be performed for FBC, ALT, Creatinine and exploratory immunology as outlined in Section 10.3.

D90 (+/- 14 days)

Medical history, temperature monitoring +/- physical examination will be performed and recorded in the CRF. Any solicited and unsolicited AEs will be recorded. Venepuncture will be performed for FBC, ALT, Creatinine and exploratory immunology as outlined in Section 10.3.

D300 (+/- 28 days)

Medical history, temperature monitoring +/- physical examination will be performed and recorded in the CRF. Any solicited and unsolicited AEs will be recorded. Venepuncture will be performed for FBC, ALT, Creatinine and exploratory immunology as outlined in Section 10.3.

Medical history and physical examination directed towards specific AEs may be performed at various other time-points throughout the study, at the discretion of investigators.

10.2. Concomitant Therapy

The following data are collected for concomitant medications:

Name Dose and frequency Start and stop dates Indication

10.3. Laboratory Evaluations

10.3.1. Clinical Laboratory Evaluations

FBC, ALT, Creatinine – Screening, D14, D56, D63, D90, D300. HIV ELISA (Murex) +/- Hexagon and Peptilav (for positives only) +/- PCR for indeterminate results – Screening.

HLA testing – D0

Screening dipstick Urinalysis blood and protein

10.3.2. Special Laboratory Evaluations

Ex vivo IFN-γ ELISPOT +/- ICS +/- *Cultured* IFN-γ ELISPOT – D0, D14, D 56, D63, D90, D300 TRAP ELISA – at the discretion of investigators Anti-AdCh63 neutralising antibody – D0 and additional time-points at the discretion of investigators

Plasma and cells will be stored at -20°C and -192°C respectively. *Ex vivo* ELISPOTs are currently being performed in the laboratory at the MRC, Fajara and results are validated by rigorous use of negative and positive controls. This technique uses an overnight stimulation by antigen of separated lymphocytes from the volunteer's blood sample to count the number of interferon gamma producing cells. Analysis by FACS,

where sufficient numbers of lymphocytes are isolated, will allow further characterisation of the response, by co-staining lymphocytes with CD4 and CD8 as well as IFN gamma. This may be performed on fresh or frozen cells.

Other immunology studies, including gene expression studies as an exploratory analysis, may be performed at the time-points in the schedule of attendances at the discretion of investigators.

A sample of blood from venepuncture on Day 0 will be stored for later testing by polymerase chain reaction (PCR) for *Plasmodium falciparum*.

11. Assessments and Evaluations

11.1. Definition of criteria

11.1.1. Primary Evaluation Criteria

Assessment of safety and tolerability.

11.1.2. Secondary & Tertiary Evaluation Criteria

Assessment of immunogenicity.

11.2. *Parameters to be recorded*

Safety:

The following solicited AEs (Table 1) will be recorded in the AE section of the CRF.

	Adverse events		
Local (injection site)	Pain at the injection site		
	Redness/Discolouration at the injection site		
	Swelling at injection site		
	Warmth at the injection site		
	Itch at the injection site (not for group 2/3)		
	Scaling/Pustules/Blistering at injection site		
	Limitation of arm movement (group 2/3)		
General – Adults	Documented fever (Axillary temperature > 37.5° C)		
	Symptoms of feverishness		
	Malaise		
	Arthralgia		
	Headache		
	Myalgia		
	Nausea / vomiting		
	Other (specify)		
General – Children aged 2-6	Documented fever (Axillary temperature > 38° C)		
	Reported fever by carer		
	Reduced oral intake		
	Reduced activity		
	Vomiting		

Table 1: Solicited local and general adverse events documented in the CRF

11.3. Method and Timing of measurements

11.3.1. Definitions

Definitions for the terms adverse event (or experience), adverse reaction, and unexpected adverse reaction have previously been agreed to by consensus of the more than 30 Collaborating Centres of the WHO International Drug Monitoring Centre (Uppsala, Sweden). Although those definitions can pertain to situations involving clinical investigations, some minor modifications are necessary, especially to accommodate the pre-approval, development environment.

The following definitions, with input from the WHO Collaborative Centre, have been agreed:

11.3.2. Adverse Event

Any untoward medical occurrence in a clinical investigation subject occurring in any phase of the clinical study whether or not considered related to the vaccine. This includes an exacerbation of pre-existing conditions or events, intercurrent illnesses, or vaccine or drug interaction. Anticipated day-to-day fluctuations of pre-existing conditions, including the disease under study, that do not represent a clinically significant exacerbation will not be considered adverse events. Discrete episodes of chronic conditions occurring during a study period will be reported as adverse events in order to assess changes in frequency or severity.

Adverse events will be documented in terms of a medical diagnosis(es). When this is not possible, the adverse event will be documented in terms of signs and symptoms observed by the investigator or reported by the subject at each study visit.

Pre-existing conditions or signs and/or symptoms (including any which are not recognised at study entry but are recognised during the study period) present in a subject prior to the start of the study will be recorded on the Medical History form within the subject's CRF.

11.3.3. Adverse Reactions

In the pre-approval clinical experience with a new medicinal product or its new usages, particularly as the therapeutic dose(s) may not be established, all noxious and unintended responses to a medicinal product related to any dose should be considered adverse reactions.

The phrase "responses to a medicinal product" means that a causal relationship between a medicinal product and an adverse event is at least a reasonable possibility, *i.e.* the relationship cannot be ruled out.

11.3.4. Unexpected Adverse Reactions

An adverse reaction, the nature or severity of which is not consistent with the applicable product information (*e.g.* Investigator's Brochure for an unapproved investigational medicinal product) is considered as an unexpected adverse reaction.

11.3.5. Serious Adverse Events

A serious adverse event (experience) or reaction is any untoward medical occurrence that at any dose:

- results in death,
- is life-threatening,

Note: The term "life-threatening" in the definition of "serious" refers to an event in which the patient was at risk of death at the time of the event; it does not refer to an event which hypothetically might have caused death if it were more severe.

- requires inpatient hospitalisation or prolongation of existing hospitalisation,
- results in persistent or significant disability/incapacity, or •
- is a congenital anomaly/birth defect. •

Medical and scientific judgment should be exercised in deciding whether expedited reporting is appropriate in other situations, such as important medical events that may not be immediately life-threatening or result in death or hospitalisation but may jeopardise the patient or may require intervention to prevent one of the other outcomes listed in the definition above. These should also usually be considered serious.

11.3.6. **Collection of Adverse Events**

At each visit vital signs will be documented on the CRF together with local reactions at the injection site. The largest diameter through the injection site of any redness will be recorded in millimetres. The largest diameter through the injection site of local swelling, defined as a more generalized swelling of the deltoid muscle will be recorded in millimetres. Severity of these local findings will be graded using the scale given in Table 2.

Table 2: Grading a) for swelling			
Grade	Diameter [mm]		
0	0		
1	< 20		
2	20 – 50		
3	> 50		

b) for redness		
Grade	Diameter [mm]	
0	0	
1	< 50	
2	50 – 100	
3	> 100	

Study subjects/carers will be asked to indicate the maximum degree of pain they experience at the injection site using a scale ranging from 0 to 3 as described in Table 3.

Grade	Description		
0	No pain at all		
1	Painful on touch, no restriction in movement of arms, able to work, drive, carry heavy objects as normal		
2	Painful when limb is moved		
	(i.e. restriction in range of movement in arm, difficulty in carrying objects)		
3	Severe pain at rest		
	(i.e. unable to use arm due to pain.)		
Limitation of arm movement			
Grade	Description		
0	No limitation (> 180 degrees)		
1	Limitation to < 180 degrees		
2	Limitation to < 90 degrees		
3	Limitation to < 30 degrees		

All local reactions will be considered causally related to the vaccination.

At each visit subjects will be requested to report local and general side effects they might have experienced since they last were seen. These will only be recorded in the CRF if they occurred up to 30 days post vaccination, unless they meet the criteria for serious adverse event as outlined below. The investigator will assess the severity of the solicited signs and symptoms using the key provided in Tables 4 and 5.

GRADE 0	None	
GRADE 1	Mild: Transient or mild discomfort (< 48 hours); no medical intervention/therapy	
	required	
GRADE 2	Moderate: Mild to moderate limitation in activity - some assistance may be needed; no	
	or minimal medical intervention/therapy required	
GRADE 3	Severe: Marked limitation in activity, some assistance usually required; medical	
	intervention/therapy required.	

Table 4: Intensity of the general adverse events in adults will be assessed	as described.
Table 4: Intensity of the general adverse events in adults will be assessed	as described:

Table 5: Intensity of the general adverse events in children (aged 2-6) will be assessed as described:

Systemic (General)	Grade 1	Grade 2	Grade 3
Fever (axillary temp)	≥38C- ≤39C	≥39C - ≤40C	≥40C
Decreased oral intake	Minimal decrease in oral	Below 50% of normal	No oral intake in
	intake	oral intake in 24 hr	24hr
Vomiting	1 episode in 24hr; no	2-3 episodes in 24 hr	> 3 episodes in 24
	interference with activity	OR some interference	hours OR prevents
		with activity	daily activity
Diarrhea	Unformed stool OR 1-3	Partially liquid stools	Completely liquid
	more stools than	OR 4-6 more stools	stools OR >6 more
	baseline in 24 hr	than baseline in 24hr	stools than baseline
			in 24 hr
Reduced activity	Minimal interference	Below 50% of normal	Prevents daily
	with activity	activity in 24 hr	activity
Unsolicited adverse	Minimal interference	Below 50% of normal	Prevents daily
events	with activity	activity in 24 hr	activity

Activity for the purposes of this assessment will be considered oral intake, sleep and play.

The investigator using the guidelines provided in section 11.3.8. will assess the relationship of the event to the administration of the vaccine. Both severity of the event and its relationship to the vaccine administration will be documented in the CRF if occurring up to 30 days post vaccination for groups 2 and 3, unless it fulfils criteria for a serious adverse event (section 11.3.5).

Further details for any AE (such as start/stop date and any treatment) will also be gathered, regardless of the relationship to the vaccine in sufficient detail to also allow assessment of the AE according to case definitions published by the Brighton Collaboration [62]. Space is allocated on the CRF to document any unsolicited adverse event reported by the volunteer/carer up to day 30 post-vaccination for groups 2 & 3, and throughout the study period for group 1. Serious adverse events (SAE) as defined in section 11.3.5 of the protocol will be documented in the CRF and reported as described.

Adverse events will not be collected on volunteers in groups 2 and 3 given rabies vaccine at the end of the trial.

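### The note under Table 5 counts oral intake as activity, so a child who only eats less is also recorded with reduced activity, a separate solicited event

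*Protocol*

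**What the plan says.** Protocol section 11.2, Table 1, lists the solicited general events for children aged 2-6. Two of them are "Reduced oral intake" and "Reduced activity", on separate lines.

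Section 11.3.6, Table 5, grades the intensity of these events, again on separate rows (the intake item is called decreased oral intake there). Grade 1 on the intake row begins "Minimal decrease in oral" intake. Grade 1 on the activity row begins "Minimal interference" with activity. The vomiting row also refers to activity in each grade, and the row for unsolicited events is graded on activity alone.

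The note under the table defines the term for all of these rows: "Activity for the purposes of this assessment will be considered oral intake, sleep and play".

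Section 9.3 has each solicited side effect classified on a four-level scale from none to severe. Section 4.3.1 places solicited events in the primary endpoint. Section 12.5 plans no formal statistical analysis, and section 13.2 provides for a descriptive tabulation of adverse events.

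**The concern.** Table 1 treats feeding and activity as different things to ask about. The note makes one a component of the other. A carer who reports only that the child is eating less has, by the protocol's own definition, also reported a reduction in activity. The reduced-activity row then combines feeding, sleep and play, and its name no longer tells the reader what was lost.

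In a descriptive safety study the rows of the solicited-event table are the result. Section 12.1 intends comparisons of tolerability between two doses of AdCh63 ME-TRAP and, in children, two doses of MVA ME-TRAP. The 14-day safety profiles in section 4.4.1 draw on the same events. At stake is whether one line of those tables carries information of its own or partly repeats another line.

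**Working it through.** The protocol states no figure on this point, so there is nothing to reproduce. The check sets the definitions side by side and then bounds the effect.

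**Step 1. A child who eats slightly less but plays and sleeps normally.**

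| Table 5 row | Grade 1 criterion | Met? |
|---|---|---|
| Decreased oral intake | Minimal decrease in intake | Yes |
| Reduced activity, with activity including oral intake (the note) | Minimal interference with activity | Yes, through intake |
| Reduced activity, with activity meaning sleep and play only | Minimal interference with activity | No |

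One symptom fills two rows under the note and one row without it.

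**Step 2. Does anything else in the protocol remove the overlap?** Section 11.3.2 prefers a diagnosis to a list of symptoms, but section 9.3 still has every solicited item classified, so the rows are not merged. No rule excludes oral intake from the activity row once it has been recorded on its own row, and none bars scoring both.

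**Step 3. How far up the grades does this go?** Only grade 1 is certain. Grade 2 activity requires less than half of normal activity, and grade 3 requires that daily activity be prevented. The protocol does not say how intake, sleep and play combine, so feeding loss alone may or may not reach those levels.

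**Step 4. Size.** Let p be the proportion of children with reduced play or sleep and q the proportion with reduced intake. Under the note, the recorded proportion with reduced activity is the proportion with either:

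- lower bound (complete overlap): max(p, q)
- upper bound (no overlap): p + q, if this does not exceed 1
- if independent: 1 − (1 − p)(1 − q)

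The protocol gives neither p nor q. The values below are assumptions for illustration.

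| Assumed p | Assumed q | Lower bound | Independent | Upper bound | Sleep and play only |
|---|---|---|---|---|---|
| 10% | 20% | 20% | 1 − 0.90 × 0.80 = 28% | 30% | 10% |
| 20% | 30% | 30% | 1 − 0.80 × 0.70 = 44% | 50% | 20% |

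Because the lower bound is max(p, q), recorded reduced activity can never fall below recorded reduced intake.

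**Step 5. Scale.** Each paediatric arm has 6 children (section 4.2), so one child is 1/6, or about 17 percentage points. In the first illustration the excess of 10 to 20 points is roughly one child per arm.

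**Step 6. What does not move.** A child with reduced intake already has a solicited general event. Adding a second row for the same child leaves the proportion with at least one such event unchanged.

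**The case against.** The strongest reply is that Table 5 is an intensity key, while Table 1 decides what is solicited, and Table 1 keeps the two events apart. A field worker might therefore score reduced activity only when play or sleep has fallen. That reading is possible, but the protocol does not state it. The row and the note together say otherwise, so the recorded value would depend on who reads the form.

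Other parts of the reply stand in full, and they rule out stronger conclusions that a reader might infer:

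- **That counts, proportions and grades are inflated throughout.** They are not. Step 6 shows that the proportion with any solicited general event is unaffected, and the protocol nowhere sums solicited events into a score.
- **That the vomiting grades are wrong.** Vomiting is grade 1 with "1 episode in 24hr; no" interference with activity; grade 2 adds the alternative "OR some interference" with activity, and grade 3 has the alternative "hours OR prevents" daily activity. One vomit followed by a smaller meal does move from grade 1 to grade 2. But grading vomiting, or an unsolicited illness, by whether it stops a young child eating is a coherent measure of severity and may be intended.
- **That the overlap biases the comparison between arms or doses.** The same definition applies in arms A, B and C, and the protocol gives no rates of appetite loss by arm. If feeding did differ between arms, the difference would be real and would appear on two rows.
- **That a safety decision turns on it.** Progression between stages rests on review by the DSMB and the Ethics Committee (section 4.4.1) and on the absence of safety concerns (section 8.5). Discontinuation rests on new information, vaccine-related SAEs or investigator discretion (section 4.4.2). None of these has a numerical threshold that a duplicated grade 1 event could cross.

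One might add that the intake row shows which children are double-recorded. That helps only in part: if the CRF holds a single activity grade, whether play or sleep also fell cannot be recovered afterwards.

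**Conclusion.** The point holds in a narrow form. As written, the note makes reduced feeding sufficient for at least grade 1 reduced activity. That row is then bounded below by the intake row and does not separately measure loss of play or sleep. The effect is limited to the reduced-activity row and to any tally of events in the descriptive tables and the 14-day safety profiles. No hypothesis test is involved.

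The logical overlap rests only on the protocol's text. Its size rests on assumed rates, and the range in Step 4 needs no assumption about how the symptoms are associated. The importance is modest, but the item belongs to the primary safety endpoint and the wording is easy to put right before data are collected.

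**What to change.** Amend the note under Table 5 so that, for the reduced-activity row only, activity means sleep and play, and oral intake is graded in its own row. Leave the present definition in force for the vomiting and unsolicited-event rows. Put the same wording in the CRF before the first paediatric vaccination.

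The cost is one line in the table and matching text in the CRF, with no extra data. The small downside is that Table 5 then carries a row-specific definition of activity, so the note must name the rows to which each definition applies.

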11.3.7. Follow-up of Adverse Events

Adverse events possibly, probably or definitely related to the vaccine, whether serious or not, which persist at the end of the trial will be followed up by the investigator until their complete resolution or stabilisation. Moreover, any serious adverse event possibly, probably or definitely related to the vaccine and occurring after trial termination should be reported by the investigator according to the procedure described below. Outcome of any non-serious adverse event occurring within 30 days post-vaccination or any SAE reported during the entire study will be assessed as:

- Recovered/resolved
- Not recovered/not resolved
- Recovering/resolving
- *Recovered with sequelae/resolved with sequelae*
- Fatal (SAEs only)

Subjects who have moderate or severe on-going adverse events at the completion of the study will be advised to consult a physician if the event is not considered to be related to the study vaccine. A follow-up visit will be arranged to manage the problem and to determine the severity and duration of the event, if it is considered to be related to the study vaccine. If appropriate, specialist review will be arranged by MRC investigators.

